6.2.2 Secondary efficacy variables

The secondary efficacy variables are defined in the following. The confirmatory analysis of selected secondary efficacy variables will be performed only for data from TP1. In addition, secondary efficacy variables will be analyzed descriptively for both treatment periods.

• Heavy menstrual bleeding (HMB) response: HMB response is defined as MBL <80.00 mL during last 28 days of treatment and >50% reduction from baseline (assessed by AH method). Missing AH data will be imputed as explained in Section 4.3.

If an endometrial biopsy was conducted, bleeding on the day of intervention and the 3 days thereafter will not be considered in this evaluation, i.e., bleeding/'spotting' on the day of biopsy and 3 days thereafter will not be considered as day(s) with bleeding/'spotting' and AH values will be set to 0 mL.

After imputing missing bleeding intensities and AH values (see Section 4.3) and considering potential biopsies, the 28-day period will be extended in case there are still any AH values missing in the last 28 days (similar to the description in Section 6.2.1 b); a) will not be applied). Based on the 28-day period a subject will be considered as not being an HMB responder if

- i) the sum of the non-missing (i.e., original or imputed) AH values is \geq 80.00 mL *or* the reduction of blood loss is \leq 50% as compared to baseline or
- ii) the subject did not complete at least 8 weeks of treatment.

If neither of i) or iii) applies, the subject will be considered as an HMB responder.

• Time to onset of amenorrhea: Onset of amenorrhea is defined by the first day for which the MBL for all subsequent 28-day periods up to the end of a treatment period is <2 mL (amenorrhea defined similar to primary endpoint). The first 28 days with non-missing AH values until the last 28 days with non-missing AH values under treatment will be considered for deriving the time to onset of amenorrhea. An analogous approach as described for amenorrhea in the last 28 days of treatment (Section 6.2.1) will be applied to assess the amenorrhea status for each of the subsequent, overlapping 28-day periods within a treatment period (except for criterion iii), which does not apply). The censoring mechanism is assumed to be non-

informative and the subjects will be handled as right-censored, if applicable. If a subject completed the 84 days of a treatment period and did not experience an onset of amenorrhea, the subject will be censored on Day 57 of the treatment period.

For prematurely discontinued subjects, censoring also depends on whether an onset of amenorrhea can be ruled out or not during the time the subject was in the respective treatment period. An onset of amenorrhea can be ruled out if in the last 28-day period before the subject discontinued the respective treatment period, the sum of AH values exceeds 2 mL. If this is not the case, then an onset of amenorrhea cannot be ruled out for the respective treatment period. Thus, there are in principle the two possibilities:

• In case the subject discontinued from the respective treatment period prematurely and an onset can be ruled out, subjects will be treated as right-censored at the first day of the last 28-day period after which AH bleeding values for all further days are missing (see Figure 6–3 (a)).

If the subject prematurely discontinued from the respective treatment period but an onset cannot be ruled out, the subject will be censored on the day before the first day of the first 28-day period which indicates that an onset may have taken place (see Figure 6-3 (b)).

- Time to onset of controlled bleeding: Onset of controlled bleeding is defined by the first day for which the MBL for all subsequent 28-day periods up to the end of a treatment period is <80.00 mL. The first 28 days with non-missing AH values until the last 28 days with non-missing AH values under treatment in the respective treatment period will be considered for deriving the time to onset of controlled bleeding. An analogous approach as described for HMB response (Section 6.2.2) will be applied to each of the subsequent, overlapping 28-day periods within a treatment period (except for criterion ii), which does not apply). Time to onset of controlled bleeding is then derived analogous to time to onset of amenorrhea.
- Absence of bleeding (spotting allowed) during last 28 days of treatment (assessed by the UF-DBD): Absence of bleeding is defined as no scheduled or unscheduled bleeding during the last 28 days of a treatment period based on the UF-DBD. Missing data will be imputed as described in Section 4.3. The last days under treatment with 28 days with non-missing bleeding eDiary data will be used to calculate whether absence of bleeding occurred. Thus, if the last 28 days of treatment include days with missing bleeding eDiary data, the left margin of this interval will be displaced backwards in time and step-wise until the required number of 28 non-missing values are included. The left margin may be displaced backwards at maximum up to the end of the first bleeding episode when treatment was started in respective treatment period.

If an endometrial biopsy was conducted, bleeding on the day of intervention and the 3 days thereafter will not be considered in this evaluation, i.e. bleeding on the day of biopsy and 3 days thereafter will not be considered as day(s) with bleeding and UF-DBD values will be set to 'no vaginal bleeding'.

Subjects who discontinue treatment prior to completion of 8 weeks of treatment will be considered as not experiencing absence of bleeding.

[figure not shown]

Figure 6–3: Illustration of censoring rules for subjects prematurely discontinuing a treatment period.

An illustration of censoring for a subject who both discontinued on Day 31 of a treatment period. (a) The onset of amenorrhea during the subject's treatment period can be ruled out (MBL \geq 2mL in last 28-day period), and the subject is censored at the first day of her last 28-day period. (b) An onset of amenorrhea on Day 3 cannot be ruled out (MBL < 2mL in her last 28-day period(s)), and the subject is censored on Day 2.

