### **10.3.3 Missing data/drop outs**

*This section was changed in Amendment 1, see Section 15.1.1*

For the primary efficacy variable and secondary efficacy variables included in the testing strategy described in Section 10.3.2.2, it is assumed that data measured with the AH method will be only available on days when vaginal bleeding occurred. To differentiate missing AH data and days without vaginal bleeding the bleeding intensity collected in the UF-DBD will be used.

Missing bleeding data in the subject diaries will be imputed. For the UF-DBD, the worst case approach will be used for missing bleeding intensity for the single or two consecutive missing days (i.e., the maximum of the bleeding intensities of the day before and the day after the missing day[s] will be assumed).

If an endometrial biopsy was conducted during the time period under treatment, bleeding on the day of biopsy and the 3 days thereafter will not be considered as day(s) with bleeding/spotting and the AH value will be set to 0 mL. For the primary efficacy variable amenorrhea and the secondary efficacy variable HMB response, subjects will be defined as not having amenorrhea/not being a HMB responder if they did not complete at least 8 weeks

of treatment. Generally, in case a daily bleeding intensity is recorded with the UF-DBD as “no vaginal bleeding” or “spotting”, the missing AH value for this day will be set to 0 mL.

For days with bleeding intensity of “mild” or higher in the UF-DBD, missing AH values will be replaced by the mean value of AH values of the days with the same bleeding intensity. In case there are no AH values with the same bleeding intensity, the mean of the AH values of next higher intensity will be used. In case there is no intensity higher than the bleeding intensity of the missing AH values available, either, no replacement for the missing AH values will be done for such days; but if at least one such day occurs within the respective 28 days of treatment for a subject, the subject will be considered as not having amenorrhea/not being a HMB responder.

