Furthermore, the last days under treatment with at least 28 days with non-missing bleeding intensity/AH values under treatment until the initial bleeding episode when the treatment started (after the imputations above) (without missing information: Days 57 to 84 under treatment) will be used to calculate the primary efficacy variable and the secondary efficacy variable HMB response. After these imputations a subject will be considered as not having amenorrhea in the presence of missing AH values if the sum of all non-missing AH values is not lower than 2 mL or if for missing AH values the bleeding intensity in the UF-DBD is “mild” or higher, otherwise the subject will be considered as having amenorrhea. An equivalent approach as described for the amenorrhea rate will be applied for the secondary variable HMB response, ie, after the imputations as described above a subject will be considered as not being a HMB responder in the presence of missing AH values if the sum of all non-missing AH values is  $\geq 80$  ml or the reduction of blood loss is  $\leq 50\%$  as compared to baseline or if for missing AH values the bleeding intensity in the UF-DBD is “mild” or higher, otherwise the subject will be considered as a HMB responder.

For the secondary variables onset of amenorrhea and onset of controlled bleeding the first 28 days with non-missing bleeding/AH values until the last 28 days with non-missing bleeding/AH values under treatment will be considered. An analogous approach as described above for the primary efficacy variable and the secondary efficacy variable HMB response will be applied to assess the bleeding status for each of these 28-day windows in terms of amenorrhea and controlled bleeding. If a subject does not achieve amenorrhea or controlled bleeding until end of treatment the subject will be considered as censored for the respective endpoint.

Sensitivity analyses will be conducted to evaluate the impact of missing data. These will be described in the SAP.

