4.3.1 Bleeding data

The following rules for the handling of missing vaginal bleeding data pertains to bleeding data assessed by the AH method, the menstrual pictogram (MP, see Appendix 1) or the item "Rate the severity of **any vaginal bleeding** in the past 24 hours" (on a 6-point Likert scale) in the Uterine Fibroid Daily Bleeding Diary (UF-DBD, see Appendix 2). The resulting data forms the basis for the primary, the secondary and bleeding-related other efficacy variables (see Section 6.2).

On days without bleeding, no collection of sanitary products for the AH value determination was asked for. The UF-DBD is used for the identification of these non-bleeding days. Thus, missing AH/MP values on days where the UF-DBD recorded the bleeding intensity as "No vaginal bleeding" or "Spotting" will be set to 0 mL.

Missing bleeding data in the subjects' diaries will be imputed. First, missing bleeding intensities in the UF-DBD will be imputed. Missing bleeding intensities will only be imputed if values are missing for a single or for two consecutive days. For the UF-DBD, a type of 'worst case approach' will be used for imputing missing bleeding intensities. The approach consists in replacing the missing value(s) by the maximum of the bleeding intensities of the day before and the day after the day(s) with missing value(s).

After having imputed missing values in the UF-DBD, missing AH/MP values are imputed in the next step.

For days with bleeding intensity of 'mild' or higher in the UF-DBD, missing AH/MP values will be replaced by the mean value of AH/MP values of the days with the same bleeding intensity. In case there are no AH/MP values with the same bleeding intensity, the mean of the AH/MP values of next higher intensity will be used. In case there is no intensity higher than the bleeding intensity of the missing AH/MP values available, no replacement for the missing AH/MP values will be done for such days, but if at least one such day occurs within the respective 28 days of treatment for a subject, the subject will be considered as not having amenorrhea.

In case blood loss could not be measured by the vendor for a sanitary product, the missing value will be replaced by the mean blood loss measured for the same type of sanitary product for this specific subject.

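### SAP 6.2.2 omits the protocol rule that an unmeasured, non-imputable bleeding day means HMB non-response, so the two documents can classify the same subject differently in confirmatory tests 2 and 4

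*SAP*

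**What the plan says.** **Protocol 10.3.3** gives the rule twice. If a day of intensity 'mild' or higher has a missing AH value that cannot be replaced, and it falls in the 28 days being assessed, "the subject will be considered as not having amenorrhea/not being a HMB responder". The later HMB paragraph repeats this as a third ground for non-response, beside the 80 mL and 50% limits, and ends "otherwise the subject will be considered as a HMB responder". For the onset variables, an analogous approach is "applied to assess the bleeding status for each of these 28-day windows in terms of amenorrhea and controlled bleeding".

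**SAP 4.3.1** repeats the imputation steps but attaches the consequence to amenorrhea alone: "28 days of treatment for a subject, the subject will be considered as not having amenorrhea". SAP 6.2.1 keeps it for amenorrhea, as step (a) and as criterion ii).

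**SAP 6.2.2**, for HMB response, extends the window if there are still "any AH values missing in the last 28 days (similar to the description in Section 6.2.1 b); a) will not be applied". It then lists two grounds for non-response: the volume/reduction limits, and fewer than 8 weeks of treatment. It closes with "If neither of i) or iii) applies, the subject will be considered as an HMB responder", although the list has no item iii). Time to onset of controlled bleeding takes over the HMB approach.

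HMB response is the second and onset of controlled bleeding the fourth of the four tests in the fixed sequence (SAP 6.2). The visible text of SAP Section 7 lists four added descriptive variables and nothing on this rule.

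**The concern.** The days in question are known bleeding days, because the subject recorded at least mild bleeding. Only the volume is unknown, and no value is available to impute it. The protocol resolves the doubt against response. The SAP passes over the day and takes an earlier one in its place, so the recorded bleeding adds nothing to the sum. The affected days tend to be the heavier ones, since imputation fails only where no AH value exists at that intensity or above.

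For a given subject the difference works one way. It can turn a protocol non-responder into a SAP responder, or make onset of controlled bleeding earlier or uncensored. Two governing documents then give different outcomes for the same data in two confirmatory tests. If the conflict is found after unblinding, choosing between the rules will look data-driven.

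**Working it through.** The point rests on no figure in the plan, so the check compares the rules, applies both to constructed subjects, and then asks how many reclassifications would change a test.

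**1. Which part differs.** Backward extension is common to both documents: the protocol also uses "the last days under treatment with at least 28 days with non-missing bleeding intensity/AH values under treatment". The difference is the extra ground for non-response.

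| Day in window, after imputation | Protocol, HMB | SAP, HMB | SAP, amenorrhea |
|---|---|---|---|
| Diary and AH both missing | extend | extend | extend |
| Diary 'mild' or higher, AH missing | non-responder | extend, day not counted | no amenorrhea |

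**2. Test 2, one subject (assumed values).** Baseline is 160 mL and 55 mL is measured in the window. One 'very severe' day has AH missing and nothing to impute from. Protocol: non-responder. SAP: an earlier day with x mL replaces it, so sum = 55 + x and reduction = 1 − (55 + x)/160.

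- x = 0: 55 mL, 65.6%, responder
- x = 10: 65 mL, 59.4%, responder
- x = 25: 80 mL, 50.0%, non-responder

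The documents disagree for x below 25 mL. At the extreme, assume a 200 mL baseline and no other bleeding: one, five or ten such days all give a SAP responder at 0 mL and a protocol non-responder.

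**3. Test 4, one subject (assumed: 84 treatment days, calendar windows, every measured window below 80 mL).** Windows start on Days s = 1 to 57 and cover s to s + 27. A window contains Day d if d − 27 ≤ s ≤ d. Under the protocol's analogous rule, one such day on Day d ≤ 56 puts onset on Day d + 1 (Day 30 gives Day 31). With d ≥ 57 there is no onset, and by SAP 6.2.2 she is censored on Day 57. If the SAP simply skips the day, an onset on Day 2 stays on Day 2. This depends on the window handling. The backward extension stops at the end of the initial bleeding episode, and the SAP does not say what happens when there is no room to extend.

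**4. Reclassifications needed to lose a test.** Inputs: planned 104 v 52 (A1 + B2 v B1) and regions 50/25/25 (protocol 10.4). Rates also come from protocol 10.4, used as assumptions: HMB response 90% v 33%, controlled bleeding 97% v 49%. Placebo is left unchanged, and vilaprisan subjects are moved one at a time.

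Test 2 uses the continuity-corrected CMH test of SAP 6.2.1.1, critical value 3.841:

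- 93 v 17 responders: chi-square 50.0; 41 of 93 must revert.
- 20% dropouts counted as non-responders (0.8 × 90% = 72%; 0.8 × 33% = 26.4%), 75 v 13: chi-square 28.8; 31 of 75 must revert.

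Test 4 uses the stratified logrank test of SAP 6.2.2.1, critical |Z| 1.96, with vilaprisan events on Day 2 and non-events censored on Day 57:

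- 100 v 25 events: Z = 9.35 with placebo onsets spread over Days 2–56, or 7.03 with all on Day 2; 38 or 33 must become censored.
- 20% dropouts counted as no onset, 80 v 20 events: Z = 5.17 or 4.68; 26 or 23 must become censored.

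**5. Smaller achieved size.** Protocol 10.4 says the planned size was not reached; the achieved size is not given. Approximate unstratified power of test 2 if 0, 10 or 20% of vilaprisan responders revert: 0.998, 0.967, 0.840 with 40 v 20 subjects; 0.985, 0.905, 0.720 with 30 v 15.

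**The case against.** **The SAP rule is open and arguable.** SAP 6.2.2 states it in the endpoint definition, the SAP is to be approved before database release, and one unmeasured day matters less against 80 mL than against 2 mL. All of this stands. A reader might infer a concealed change; the text does not support that. What is missing is a statement that the rule departs from protocol 10.3.3, with a reason. The visible Section 7 gives none, though it may not be the complete section.

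**The trigger is narrow.** Under both documents "missing AH/MP values will be replaced by the mean value of AH/MP values of the days with the same bleeding intensity" (AH only in the protocol), failing which a higher intensity is used. On the natural reading, imputation fails only if no AH value exists at the same or any higher intensity. The SAP also fills in unmeasurable products and allocates undated AH values to bleeding days. Eligibility required two AH-measured episodes above 80 mL, so a within-subject pool that includes screening would usually hold heavy-day values. If the pool is across subjects, the trigger is almost empty. Neither document defines the pool. This stands and limits the size.

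**Sensitivity analyses may cover it.** It is tempting to say that no planned analysis tests the rule. That is too firm. SAP 6.2.2.2 places the secondary sensitivity analyses on the PPS but refers to all of 6.2.1.2, which includes the multiple-imputation analysis. Protocol 10.3.3 also promises missing-data analyses, and the PPS criteria, set elsewhere, might exclude such subjects. Still, the multiple imputation is written for amenorrhea only, and none is specified for HMB response or controlled bleeding.

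**The phrase 'similar to 6.2.1 b)' might import criterion ii).** It describes the window extension, and 6.2.2 then gives its own list without that criterion.

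**Conclusion.** The two documents conflict on a classification rule for HMB response and, by reference, for onset of controlled bleeding. The same subject can have different outcomes under each in tests 2 and 4. This is a minor to moderate protocol–SAP reconciliation.

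Two stronger inferences are not supported. First, a bias towards vilaprisan: the rule is the same in both arms, and placebo subjects are expected to bleed more, so the direction between arms is not fixed. Second, a changed conclusion: at planned size and the assumed rates, 31 to 41 vilaprisan responders (test 2) or 23 to 38 events (test 4) would have to revert with placebo unchanged, for a trigger that is probably rare. The margin is smaller at the unstated achieved size, but a loss would still need substantial reclassification. The primary endpoint keeps the criterion, and study success rests on the primary endpoint alone.

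What can move is the estimated response rates, the risk difference and the onset curves. By how much depends on the number of subjects with such days, which the documents do not give. The test 4 illustration also rests on assumed window handling and on reading the protocol's analogous approach literally.

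**What to change.** Before unblinding, do one of the following.

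1. **Restore the protocol rule.** In SAP 6.2.2, add as a ground for HMB non-response at least one day in the window with diary intensity 'mild' or higher and AH missing after imputation. Extend the window only for days when diary and AH are both missing. Add the HMB consequence to SAP 4.3.1, apply the same to the controlled-bleeding windows, and renumber the list.
2. **Keep the SAP rule.** Declare and justify it in Section 7 as a departure from protocol 10.3.3. Run the protocol rule on the FAS as a sensitivity analysis for tests 2 and 4, in addition to the PPS analyses. Correct the closing reference to i) or ii).

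Under either option, report by arm the number of subjects with such days.

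The cost is a few sentences and minor programming. Option 1 may move a few subjects in either arm to non-response or to a later or censored onset. Option 2 adds one sensitivity table per endpoint.

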#### **Time to onset of controlled bleeding**

Onset of controlled bleeding is defined by the first day for which the menstrual blood loss for all subsequent 28-day periods up to the end of Treatment Period 1 is <80.00 mL. Subjects are treated as censored if they did not experience an onset of controlled bleeding during Treatment Period 1. Censoring rules will be described in more detail in the SAP.

Time to onset of controlled bleeding will be analyzed analogously to the secondary efficacy variable time to onset of amenorrhea.

The study will be considered successful if at least superiority of vilaprisan 2 mg vs. placebo after Treatment Period 1 based on the primary variable could be demonstrated.

Sensitivity analyses will be conducted for the primary efficacy variable and the first three secondary efficacy variables as applicable. These will be described in the SAP.

All primary and secondary efficacy variables will also be analyzed descriptively in frequency tables by treatment period within each treatment group, except for time to event variables which will be analyzed by treatment group using the Kaplan-Meier estimates.

Other efficacy variables will be evaluated and presented by means of descriptive statistics.

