#### 10.4 Determination of sample size

*This section was changed in Amendment 1, see Section 15.1.1*

**No longer valid, since with implementation of the protocol amendment 5, Version 5.0 no new subjects will be recruited and no study medication will be given to the subjects who have been enrolled in the study. This section describes the original sample size planning prior to the decision to temporarily pause the study. The original planned sample size has not been reached.**

Assumptions for sample size calculations were based on the ASTEROID 1 study (Study 15788) and the ASTEROID 2 study (Study 17541) with treatment durations of 12 and 24 weeks respectively.

In ASTEROID 1, amenorrhea rates (defined as MBL <2 mL during last 28 days of treatment) of about 0.7, 0.9, and 0.9 for vilaprisan 2 mg and of about 0.2, 0.0, and 0.1 for placebo for the regions US/Japan/European Union and Canada, respectively, were observed with differences between vilaprisan 2 mg and placebo of about 0.5 to 0.9. In ASTEROID 2, similar amenorrhea rates were observed with numerical variation between the treatment periods. HMB response rates in the last 28 days amounted to percentages above 90% for vilaprisan 2 mg and 33% or lower for placebo. Median onset of amenorrhea was reached on day 6 after start of treatment for vilaprisan 2 mg. Due to the low number of subjects achieving amenorrhea until end of placebo treatment no median onset of amenorrhea could be calculated for placebo. Onset of controlled bleeding was reached on day 2 after start of treatment for vilaprisan 2 mg. Again, as for onset of amenorrhea, no median onset of controlled bleeding could be calculated for placebo due to the low number of subjects achieving controlled bleeding until the end of placebo treatment. At the end of treatment controlled bleeding was reported for about 97% of subjects for vilaprisan 2 mg and for 49% of subjects for placebo, respectively.

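### Onset of controlled bleeding is defined as MBL below 80.00 mL, but its derivation borrows the HMB-response criteria and leaves the 50%-reduction rule in place, so the fourth confirmatory test can be programmed in two ways

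*SAP*

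**What the plan says.** **Definition.** Protocol 10.3.2.2 sets the event by volume alone: "menstrual blood loss for all subsequent 28-day periods up to the end of Treatment Period 1 is <80.00 mL". Protocol 10.3.1.2 gives the same definition. The SAP 6.2.2 bullet on controlled bleeding opens in the same way: "for all subsequent 28-day periods up to the end of a treatment period is <80.00 mL". None of these places compares with baseline.

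**Derivation.** The same SAP bullet continues: "An analogous approach as described for HMB response (Section 6.2.2) will be applied to each of the subsequent, overlapping 28-day periods". Its only carve-out is "except for criterion ii), which does not apply".

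**What is borrowed.** The HMB-response bullet in SAP 6.2.2 lists two ways to fail. Criterion i) is met if the summed AH values reach 80.00 mL, or if "the reduction of blood loss is" 50% or less against baseline. Criterion ii) is fewer than 8 completed weeks of treatment.

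**Role.** SAP 6.2 and protocol 10.3.2.2 make this variable the fourth and last test in the fixed sequence, using a stratified log-rank test at 0.05. Protocol 15.1.1.2 says that it entered the hierarchy to support a label claim. SAP section 7, on changes to the planned analysis, mentions no new definition.

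**The concern.** One SAP bullet carries two event definitions for a confirmatory test. The exception names a numbered criterion, which makes sense only if the numbered list is carried over. Once it is, nothing removes the reduction half of criterion i).

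For a woman who completes treatment, final-window status would then essentially repeat HMB response, which is already test 2. The reported onset times would describe a different endpoint from the protocol's. Two competent programmers could produce different event data, and the choice should not still be open at unblinding.

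**Working it through.** **1. The plan's own figure.** No sample-size figure depends on this wording, but the planned 156 is the base for the power check.
- With 52 per group and 20% dropout, 52 × 0.8 = 41.6. That is about 41 on placebo and 83 on pooled vilaprisan.
- The 156 cannot be reproduced uniquely, because the placebo rate, per-test power and hazards are not stated. It is plausible: an assumed 0.2 vs 0.6, 95% power, 1:1 and a continuity correction give 41 per arm, and 41/0.8 = 51.25, rounded up to 52.

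**2. The limit under each reading.** Let B be baseline MBL and M the MBL in one 28-day window.
- Definition: controlled if M < 80.
- Criterion i) taken whole: controlled if M < 80 and M < B/2, that is M < min(80, B/2).
- The readings differ only when B/2 ≤ M < 80, which requires B < 160 mL.

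| Baseline (mL) | Limit, definition | Limit, criterion i) whole |
|---|---|---|
| 81 | 80 | 40.5 |
| 100 | 80 | 50 |
| 120 | 80 | 60 |
| 150 | 80 | 75 |
| 160 or more | 80 | 80 |

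Entry requires more than 80.00 mL per qualifying bleed (SAP section 3), and SAP 6.1.2 plans a baseline category of 150 mL or less. Affected women are therefore expected.

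**3. Two worked cases.**
- *Lost event.* Baseline 110 mL, 60 to 75 mL in every window. The definition gives an onset. With criterion i) whole, the limit is 55 mL, no window passes, and a completer is censored on Day 57.
- *Later onset.* Baseline 100 mL, 55 mL in the first window because treatment starts on Days 3 to 7 of a bleed (protocol 7.1). The definition counts that window as controlled. With criterion i) whole it fails at the 50 mL limit, so onset moves later.

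**4. Illustrative size (assumed inputs, not document figures).** Baselines were taken as lognormal with median 130 to 220 mL and log-SD 0.4 or 0.6, cut at 80 mL. The placebo-like on-treatment/baseline ratio had median 0.9 (log-SD 0.5) or 0.6 (log-SD 0.6).
- Share with baseline below 160 mL: 21% to 66%.
- Share of single windows no longer classed as controlled: from 7.5% − 5.1% = 2.4 points to 47.0% − 33.4% = 13.6 points.

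**5. Power of test 4.** HR = ln(1 − p_v)/ln(1 − p_p), then Schoenfeld's formula with one third on placebo. Protocol 10.4 supplies the rates. The HMB-response rates serve only as a proxy for criterion i) taken whole.
- Definition: 0.97 vs 0.49. HR = ln 0.03/ln 0.51 = 5.21; events 83 × 0.97 + 41 × 0.49 = 100.6; power above 0.999.
- Proxy: 0.90 vs 0.33. HR = ln 0.10/ln 0.67 = 5.75; events 83 × 0.90 + 41 × 0.33 = 88.2; power above 0.999.

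Protocol 10.4 says that the planned size was not reached and does not give the number achieved. With only 10 evaluable women per group, the two powers would be 0.970 and 0.968. The choice of rule hardly moves power even then.

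**The case against.** **The volume-only reading is available.** The SAP bullet states the 80.00 mL definition first, and an analogous approach need not be an identical one. It could cover only imputation, biopsy days and window extension. Protocol 10.3.3 describes the step as judging each window for amenorrhea and for controlled bleeding, not for HMB response. The onset-of-amenorrhea rule, which the SAP also tells the programmer to follow, rules out an onset by volume alone. This much stands: a reader might infer that the 50% rule will certainly be applied, and the documents do not show that. They do not exclude it either. Protocol 10.3.3 places its reference after an HMB rule that contains the 50% reduction. The onset-of-amenorrhea bullet and SAP 6.2.3.1 also name exactly which borrowed elements are dropped.

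**A size might be read from protocol 10.4.** It reports: "At the end of treatment controlled bleeding was reported for about 97% of subjects for vilaprisan 2 mg and for 49% of subjects for placebo". It also reports: "HMB response rates in the last 28 days amounted to percentages above 90% for vilaprisan 2 mg and 33% or lower for placebo". A reader might take 49 − 33 = 16 points as the placebo loss, with the contrast growing from 97 − 49 = 48 to between 90 − 33 = 57 and 97 − 33 = 64 points. That is not supported. The 33% is an upper bound and the 90% a lower one. The text does not say that the rates share a study, period or handling of early stoppers. In the current plan the 8-week rule also separates the two endpoints and could explain part of the gap.

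**Inflation of the effect might be inferred.** Protocol 10.4 gives vilaprisan amenorrhea rates of about 0.7 to 0.9 in the earlier 12-week study. Such women pass either rule in the final window, so lost events probably fall mainly on placebo. Early windows differ, however. The same section puts vilaprisan's onset of controlled bleeding at day 2 but its median onset of amenorrhea at day 6, so some blood loss remains at the start. Among low-baseline women the 50% rule could delay vilaprisan onsets, which works against vilaprisan. The net direction is not shown.

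**Little else depends on it.** Test 4 is last, study success rests on the primary variable alone, and HMB response itself is untouched. All of this is correct.

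**Conclusion.** The point holds as an internal contradiction in the event definition of a confirmatory endpoint. It does not prove that the wrong rule will be run. Taken literally, the derivation replaces a fixed 80 mL limit by min(80, baseline/2), which affects only women with baseline MBL below 160 mL. Their number is not in the documents.

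Event counts, onset days and Kaplan-Meier estimates may change. The 2.4 to 13.6 points per window rest on assumed distributions and are not a forecast. Either rule, fixed in advance, keeps the 0.05 level. Planned power is above 0.999 both ways, taking the protocol's earlier rates and proportional hazards. The test decision is therefore unlikely to turn on this. What is at stake is that the reported endpoint is the one the protocol defines. It should be settled before unblinding, as a clarification and not as a threat to the study's conclusion.

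**What to change.** In the SAP 6.2.2 bullet on controlled bleeding, replace the exception with wording such as: for controlled bleeding, only the part of criterion i) concerning a sum of 80.00 mL or more applies; the 50%-reduction part of criterion i) and criterion ii) do not apply.

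If the sponsor does intend the 50% rule, the definition must change in both protocol and SAP, and SAP section 7 must list the change.

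In the same edit, correct the closing line of the HMB-response bullet, which refers to criteria i) and iii) although the list has only i) and ii).

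The cost is one SAP sentence and one line of derivation code before unblinding, with no new data.
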